6.3.7 Sensitivity Analysis

Sensitivity analysis will be carried out for possible intercurrent events such as discontinuation due to AE, lack of efficacy and use of rescue and prohibited medication. New estimands associated to each intercurrent event will be added to the already existing primary estimand accordingly.

6.3.8 Exposure to Treatment

Subjects will record each IMP or placebo administration (e.g., one drop every six hours, during 14 days) on their dispensed diaries.

Compliance is defined as the percentage of actual doses the patient instilled with respect to the number of total doses planned. The planned dose is always one drop of IMP or placebo. Compliance will be summarized categorically (<80%, ≥80% and 100%) by treatment regime. It will be calculated as follows:

Compliance of IMP/Placebo administered %= (num. of doses instilled / num. of planned doses))(ml))*100

Planned doses=56

Compliance at last visit with IMP/Placebo is defined as the percentage of actual doses the patient instilled with respect to the number of total doses planned at the time of the last visit with IMP/Placebo.

Compliance of IMP/Placebo administered % at last visit with IMP/Placebo = (num. of doses instilled / num. of planned doses at last visit with IMP/Placebo))(ml))*100

Date: 09-JUL-2021 NCT No.: NCT04246801

Planned doses at last visit with IMP/Placebo = (End date IMP/Placebo exposure – First date IMP/Placebo exposure+1)*4.

Sponsor: Laboratorios Salvat, S.A.

Study Code: CLOBOF3-16IA01

Compliance at visit 3 (day 8±1) is defined as the percentage of actual doses the patient instilled with respect to the number of total doses planned at visit 3.

Compliance of IMP/Placebo administered % at visit 3= (num. of doses instilled / num. of planned doses at visit 3) (ml))*100

Planned doses at visit 3=32

In case a scheduled dose was not administered (missed) the missed dose and the reason will be captured in the eCRF as per the patient diary and tabulated by treatment regimen.

All compliance data will be summarized and listed for the SAF.

6.3.9 Concomitant Medications

All concomitant medications/therapies will be classified according to ATC level 3 group text and generic medication name. The medications will be divided into two categories based on start date and end date: Prior Medications and Concomitant Medications: .

- Prior Medications: start date and end date before first day of IMP
- Concomitant Medications:
 - Start date before first day of IMP and end date after or on same day as first day of IMP or no end date, i.e. ongoing after first day of IMP; or
 - Start date after or on same day as first day of IMP

Within concomitant medications, a distinction will be made between rescue medication and prohibited medication.

Incomplete dates will be handled as follows:

- If the start and stop date for a concomitant medication are completely missing, it will be assumed that the medication was started before treatment and classified as Prior Medication.
- If only the start date is missing the medication will be classified as:
 - o Prior if end date is before first day of IMP
 - Concomitant if end date is on or after first day of IMP
- If only the end date is missing the medication will be classified as
 - Concomitant if start date is before or on same day as Day 15
- If the year and/or month are available, medication start in relation to the first day of IMP will be evaluated as close as possible (e.g., if only the year when the medication was started is available and ongoing is checked, the medication will be classified as a Concomitant Medication).
- If the medication was started in the same month as the first day of IMP, the medication will be classified as a Concomitant Medication.

Relative day will generally be calculated for all medications except for the ones with an incomplete start date.

Data will be listed for the SAF. Subject's medications will be presented separately for each timing (i.e. prior, and concomitant medications) in 2 summary tables. In addition, a summary table for rescue and prohibited medication will be presented distinguishing each one in a column.

Study Code: CLOBOF3-16IA01 Date: 09-JUL-2021 NCT No.: NCT04246801

In the listings will show whether the concomitant medication is rescue medication or prohibited medication.

Sponsor: Laboratorios Salvat, S.A.

Rescue medication shall be as reported as such in the eCRD. The following ATC3 codes of concomitant medication will be considered as prohibited medication if they are not classified as rescue medication (all medications will be reviewed and it will be considered whether any medication should be included or excluded in the prohibited classification):

- D07A Corticosteroids, plain
- D07B Corticosteroids, combinations with antiseptics
- D07C Corticosteroids, combinations with antibiotics
- D07X Corticosteroids, other combinations
- G01B Combinations of corticosteroids and antiinfectives for gynaecological use
- A01AC Corticosteroids for local oral treatment
- D01A Corticosteroids in combination with antifungals
- D10AA Corticosteroids, combinations for treatment of acne
- C05AA Antihemorrhoidals with corticosteroids
- S01B Antiinflammatory agents
- S02B Corticosteroids
- S02C Corticosteroids and antiinfectives in combination
- S03B Corticosteroids
- S03C Corticosteroids and antiinfectives in combination.
- H02 Corticosteroids for systemic use.
- L04A Immunosuppressants
- M01A Antiinflammatory and antirheumatic product, non-steroids
- N02BE NSAIDs in combination with paracetamol.
- M01B Salicylates in combination with corticosteroids.
- M01B Combinations of antiinflammatory/antirheumatic agents
- N02A Opioids
- Any ATC3 with ocular route except for S01A, S03A (Antiinfectives) preservative-free for prophylactic purposes and S01X (Other ophthalmologicals) preservative-free.

6.3.10 Adverse Events

AEs data are collected on the 'Adverse Events' eCRF form.

AEs will be coded according to the Medical Dictionary for Regulatory Activities (MedDRA) system, the latest version and tabulated by System Organ Class (SOC) and by Preferred Term (PT).

A Treatment-Emergent Adverse Event (TEAE) is defined as an AE observed after starting administration of IMP or placebo (see Section 6.3.1).

TEAEs will be summarized by presenting, for each treatment regimen, the number of events and the number and percentage of patients with:

Study Code: CLOBOF3-16IA01 Date: 09-JUL-2021 NCT No.: NCT04246801

Sponsor: Laboratorios Salvat, S.A.

- Any TEAE
- Any Serious Treatment Emergent Adverse Event (STEAE)
- Any TEAE of Special Interest (TEAESI)
- Any TEAE related to IMP/Placebo
- Any TEAE leading to treatment discontinuation (drug withdrawn)
- Any STEAE related to IMP/Placebo
- Any TEAESI related to IMP/Placebo

The number and percentage of TEAEs by causality and the number and percentage of mild moderate and severe TEAEs will be tabulated by SOC, PT and treatment arm. All tables with TEAEs by SOC and PT stratified by treatment regimen will only be counted by patient once within each PT.

The following tables will be provided with TEAEs by SOC and PT stratified by treatment regimen: TEAEs, TEAEs related to IMP/Placebo, TEAEs leading to discontinuation, STEAEs, STEAEs related to IMP/Placebo, TEAESI and TEAESIs related to IMP/Placebo.

TEAEs, STEAEs and TEAESIs will be tabulated by severity (mild, moderate or severe) and relationship to treatment (No: not related, unlikely related, Yes: possible, probable and certain). If a patient has more than one event with the same PT, the AE will only be counted once and the worst/maximal severity and the worst/strongest relationship will be used.

A listing of all AEs will be presented, whether treatment emergent or not. TEAEs will be flagged in this listing. A separate listing for deaths, STEAEs, AESIs and TEAEs leading to discontinuation will be provided (if any).

The following AEs (SOC, PT) of special interest (AESI) will be evaluated by Investigators at all study visits and time points (as applicable):

- IOP rise over 30 mmHg (SOC- INVESTIGATIONS, PT-INTRAOCULAR PRESSURE INCREASED)
- Pain/discomfort associated with IMP instillation (SOC-EYE DISORDERS, PT-EYE PAIN, OCULAR DISCOMFORT and related with IMP)

Additionally, a descriptive table (14.3.1.2.2) of ocular adverse events will be presented by SOC and PT.

SAF will be used for all AE related summaries.

As stated in the study protocol, treatment arms will be compared with respect to safety endpoints descriptively only. No further inferential comparison will be carried out.

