8.3.9 Adverse Events of Special Interest

The following AEs (SOC, PT) of special interest (AESI) will be evaluated by Investigators at all study visits and time points (as applicable):

- IOP rise over 30 mmHg
- Pain/discomfort associated with IMP instillation

An AESI may or may not be serious. Nevertheless, the investigator is responsible for ensuring that all AESIs are reported to the Sponsor immediately, but in any event no later than 24 hours of any site staff becoming aware of the event. Further instructions on how to report AESIs will be provided separately.

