6.3 Hypotheses and Statistical Methods

6.3.1 Definitions

Baseline	(Visit 1 (Day 1, 24 h after the cataract surgery).				
Time calculation	Differences between dates to express duration will be calculated as the final date - initial date + 1. To convert these days differences to other units, the following conversion factors will be used: 1 year = 365.25 days and 1 month = 30.4375 days.				
	Ex. Age = (informed consent date – date of birth + 1) / 365.25				
Absolute change	Absolute change from Baseline at Visit X will be calculated as:				
from Baseline	Absolute change from Baseline = Visit X - Baseline				
Percentage change	Percentage change from Baseline at Visit X will be calculated as:				
from Baseline	Percentage change from Baseline [%] = ((Visit X - Baseline)/Baseline) *100				
	In case of Baseline = 0 no percentage change from baseline will be calculated.				
Signs of ocular inflammation (yes/no)	The presence/absence of the different signs of ocular inflammation: Chemosis, Bulbar conjunctival injection, ciliary injection, corneal edema, keratic precipitates will be defined as:				
	No: grade=0 (absence)				
	Yes: grade=1, 2 or 3 (presence)				
Conversion Snellen	Step 1. Mar = Snellen Denominator/Snellen Numerator				
to LogMar	Step 2. LogMar = log (Mar)				
	Example: Snellen 20/40				
	Mar = 40/20 = 2				
	LogMar= log(2) = 0.3				
Treatment Emergent Adverse Event	Treatment Emergent Adverse Events (TEAEs) are defined as an event that emerges during treatment having been absent pretreatment or worsens relative to the pre-treatment state:				
	First dose IMP/Pacebo date ≤ start date AE ≤ last dose IMP/Placebo date				
Rescue medication	The following prohibited medications will be considered as rescue medication when administered to subjects not responding to IMP or placebo:				
	 Any systemic or local therapy with corticosteroids (other than the study drug) or immunosuppressant (except pre- surgical and/or surgical administration of 1 drop of a topical NSAID or corticosteroid, at the investigator discretion) 				

Date: 09-JUL-2021

Sponsor: Laboratorios Salvat, S.A. Study Code: CLOBOF3-16IA01

NCT No.: NCT04246801

	 Any topical ocular medication (except preservative-free antibiotics for prophylactic purposes and preservative-free artificial tears) Any systemic NSAID or opioids drugs (except occasional use of OTC formulations titrated no more than one single dose per week) 			

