14.3 SAFETY DATA

Adverse events

Table	Title	Pop	Top.Line
14.3.1.1	Summary of Treatment Emergent Adverse Events (TEAEs)	SAF	X
14.3.1.2.1	Treatment Emergent Adverse Events by System Organ Class and Preferred Term	SAF	
14.3.1.2.2	Treatment Emergent Ocular Adverse Events by System Organ Class and Preferred Term	SAF	
14.3.1.3	TEAEs by SOC and PT by worst severity	SAF	
14.3.1.4	TEAEs by SOC and PT by worst relationship	SAF	
14.3.1.5	TEAEs related to IMP/Placebo	SAF	
14.3.1.6	TEAEs leading to discontinuation	SAF	
14.3.1.7	Serious TEAEs	SAF	
14.3.1.8	Serious TEAEs related to IMP/Placebo	SAF	
14.3.1.9	TEAEs AESI	SAF	
14.3.1.10	TEAEs AESI related to IMP/Placebo	SAF	
14.3.2	Listings of Deaths Other Serious Adverse Events, and OtherSignificant Adverse Events	SAF	

14.3.3 [This title is reserved for narratives.]

Study Code: CLOBOF3-16IA01 Date: 09-JUL-2021

NCT No.: NCT04246801

Sponsor: Laboratorios Salvat, S.A.

Other Safety assessments

Table	Title	Pop	Top.Line
14.3.4.1	Absolute and Percentage change from Baseline in Vital Signs by treatment regimen. Descriptive Statistics	SAF	
14.3.4.2	Summary statistics. Change from Baseline to Day 3, Day 8, Day 15 and Day 29 compared to placebo in intraocular pressure (IOP).	SAF	X

Treatment exposure

Table	Title	Pop	Top.Line
14.3.5.1	Compliance with IMP/Placebo % (doses/amount). Descriptive statistics.	SAF	
14.3.5.2	Exposure to IMP/Placebo: Duration of treatment Number ofdoses completed/not completed, and reasons by treatment regimen. Descriptive statistics	SAF	

Concomitant medications

Table	Title	Pop	Top.Line
14.3.10.1	Summary of Prior Medications and Therapies tabulated by ATC level 3 group and generic medication name	SAF	
14.3.10.2	Summary of All Concomitant Medications (rescue and prohibited medications included) and Therapies tabulated by ATC level 3 group and generic medication name	SAF	
14.3.10.3	Summary of Concomitant Medications (Rescue and prohibited) tabulated by ATC level 3 group and generic medication name	SAF	

Sponsor: Laboratorios Salvat, S.A. Study Code: CLOBOF3-16IA01 NCT No.: NCT04246801

8.2 Listings of individual patient data and other information to be produced for the clinical study report (sections 16.1 and 16.2 according to ICH E3)

Listing	Title	Pop	Top.Line
16.1.7	Randomisation scheme	ALL	

Patient disposition

Listing	Title	Pop	Top.Line
16.2.1.1	Patient Disposition	ALL	
16.2.1.2	Screening Failures, Discontinued Subjects, Reason for Discontinuation	ALL	X
16.2.1.3	Visits dates		

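### The IOP event of special interest is selected by a preferred term with no threshold, so its count per arm can be wrong, and no output counts measured IOP against the threshold

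*SAP*

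**What the plan says.** **Definition.** Protocol 8.3.9 lists "IOP rise over 30 mmHg" as an AESI and names no coding term. It says these events "will be evaluated by Investigators at all study visits and time points", and it makes the investigator responsible for seeing that "all AESIs are reported to the Sponsor immediately", within 24 hours at most. Further reporting instructions are to come separately.

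**Selection.** SAP 6.3.10 attaches a coding rule: "IOP rise over 30 mmHg (SOC- INVESTIGATIONS, PT-INTRAOCULAR PRESSURE INCREASED". The companion AESI, instillation pain or discomfort, is given as "PT-EYE PAIN, OCULAR DISCOMFORT and related with IMP". The source is also stated: "AEs data are collected on the 'Adverse Events' eCRF form".

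**Tables and window.** AESIs are tabulated as treatment-emergent events (TEAEs) in Tables 14.3.1.9 and 14.3.1.10. SAP 6.3.1 gives the window as "First dose IMP/Pacebo date ≤ start date AE ≤ last dose IMP/Placebo date".

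**Measured IOP.** Protocol Table 1 schedules IOP at Visits -1, 1, 2, 3, 4 and 5 and at early termination. Protocol Appendix 3 records it as the mean of three valid measures. The only table of these readings is 14.3.4.2: "Summary statistics. Change from Baseline to Day 3, Day 8, Day 15 and Day 29 compared to placebo in intraocular pressure (IOP". Individual values go to Listing 16.2.11.

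**The concern.** The protocol defines this event by a number, but the SAP selects it by a label. The label depends on what the investigator enters and how it is coded, and it says nothing about how high the pressure went. The readings that would settle the matter are already in the database.

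The event matters. Protocol 8.3.10 names a rise in IOP as the expected reaction that could be severe, and Protocol 2.1.4 says the product has not yet been tested clinically in this indication. This trial therefore supplies the first clinical evidence on that risk. With 140 and 70 patients planned, a handful of misclassified cases would visibly change the percentages per arm.

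**Working it through.** The plan states no figure that depends on this rule, so there is none to reproduce. The check compares the rule with the definition, then looks at timing, the other outputs and a labelled illustration. Steps 1 and 4 treat the threshold as a level of 30 mmHg; step 5 returns to that.

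**1. Rule against definition**

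| Patient | Measured IOP above 30 mmHg | Counted in the AESI tables |
|---|---|---|
| Reported rise to 30 mmHg or below, coded to the named term, in window | no | yes |
| Reading above 30, not entered as an adverse event | yes | no |
| Reading above 30, coded to another term | yes | no |
| Reading above 30, coded to the named term, onset after last dose | yes | no |
| Reading above 30, coded to the named term, in window | yes | yes |

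The parenthesis reads as a selection rule. For the companion AESI it adds a filter (relatedness to study drug), while for IOP it adds none. Coding elsewhere is plausible, since Protocol 2.3 lists IOP elevation, ocular hypertension and glaucoma as separate events. Non-entry is possible too: Protocol 4.3.2 tells sites not to record expected post-surgical changes as adverse events.

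**2. Timing**

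- Planned doses: 4 × 14 = 56 (SAP 6.3.8). Protocol 6.2 gives one dose in clinic on Day 1 and dispenses 55 vials: 1 + 55 = 56.
- If all four doses are taken on Day 1, the last falls on Day 14. If only one to three are taken, Days 2 to 14 use 13 × 4 = 52, and the remaining one to three fall on Day 15.
- Visit 4 is Day 15 ± 2, so Days 13 to 17. It can fall inside or outside the window.
- Visit 5 is Day 29 ± 2, so Days 27 to 31. It is at least 27 − 15 = 12 days after an on-schedule last dose, so a first onset there is always outside.
- Scheduled post-baseline readings (Visits 2 to 5): 4 × 140 = 560 and 4 × 70 = 280, total 840. Visit 5 supplies 210 of them, or 25%.
- Patients who stop study drug early but keep attending, as Protocol 5.3 asks, have more readings outside the window.

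**3. Other outputs**

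SAP 6.3.2 defines summary statistics to include quartiles and the maximum, so Table 14.3.4.2 shows the upper tail of the change. It does not show how many patients passed a threshold. Listing 16.2.11 would have to be counted by hand. SAP 6.3.11 flags clinically significant vital signs in their listing but plans no such flag for IOP.

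**4. Illustration (assumed inputs)**

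Let p be the share of patients with a reading above 30 mmHg, s the share of those who reach the AESI table, and q the share of the others with a lesser rise coded to the same term. The documents give none of these. Assumed ranges: p 1–5%, s 50–100%, q 0–5%.

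Measured count = n × p. Tabulated count = n × [p × s + (1 − p) × q].

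Example, n = 140, p = 3%, s = 80%, q = 2%: measured 140 × 0.03 = 4.2; tabulated 140 × (0.024 + 0.0194) = 6.08.

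| Arm | p | Measured | Tabulated, lowest (s = 50%, q = 0) | Tabulated, highest (s = 100%, q = 5%) |
|---|---|---|---|---|
| Clobetasol, 140 | 1% | 1.4 | 0.7 | 8.33 |
| | 3% | 4.2 | 2.1 | 10.99 |
| | 5% | 7.0 | 3.5 | 13.65 |
| Placebo, 70 | 1% | 0.7 | 0.35 | 4.17 |
| | 3% | 2.1 | 1.05 | 5.5 |
| | 5% | 3.5 | 1.75 | 6.83 |

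The counts agree when s = 100% and q = 0, or when the two errors happen to cancel. Otherwise the tabulated count can be too low or too high.

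**5. Level or change**

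Protocol 8.3.9 and SAP 6.3.10 speak of a rise over 30 mmHg, while Protocol 8.3.10 speaks of IOP above 30 mmHg. Read as a change, the limit is baseline + 30. Exclusion 20 keeps study-eye baseline below 24, so that limit could approach 24 + 30 = 54 mmHg. The two readings select different patients.

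**The case against.** The strongest reply is that the threshold is applied at source. The SAP line keeps the 30 mmHg wording and adds a coding label. Investigators evaluate this event at every visit, at sites that measure the pressure, and must report it within 24 hours under instructions we cannot see. If that works perfectly and only those events are flagged, the table is right. This stands far enough that a reader should not infer that the count is wrong, only that it can be. But the SAP neither states that the threshold was applied nor checks it, and it mentions no separate marker to keep lesser rises under the same term out of the table.

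Three other strong readings also go too far:

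- That measured IOP is reduced to a mean. Quartiles, maxima and a listing are planned.
- That neither Day 15 nor Day 29 can contribute. Visit 4 can fall inside the window; only Visit 5 is clearly outside.
- That late events vanish. SAP 6.3.10 lists all adverse events, emergent or not, and AESIs separately. Table 14.3.1.2.2 may also show in-window events under another ocular term. None of these outputs gives a count per arm against the threshold.

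It is also fair to say that the last-dose cut-off affects every TEAE, and that SAP 6.3.10 words the definition more openly than 6.3.1. That is a wider issue. It matters here because it removes a scheduled IOP visit from the AESI tables although the safety endpoints in Protocol 7.4 run to Day 29.

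**Conclusion.** The point holds as a gap in definition and output. The SAP's rule can both add and lose cases relative to the protocol's numeric event, the TEAE window excludes first onsets at Visit 5 and some at Visit 4, and no planned table counts patients above the threshold.

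The size and direction of any error cannot be found from the documents. The ranges above rest on assumed rates and show only that a few patients either way would be large against expected counts of 1.4 to 7.0 in the active arm. The timing conclusion assumes a 14-day course taken on schedule.

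Safety comparisons are descriptive (SAP 6.3.10), so no hypothesis test is affected. The change should still be made, because the data exist and this is the risk the protocol singles out.

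**What to change.** 1. Reconcile Protocol 8.3.9 and SAP 6.3.10 with Protocol 8.3.10, and state whether the AESI threshold is a level or a change from baseline.
2. In the safety set, derive a flag for measured study-eye IOP exceeding that threshold. Tabulate n/N (%) by arm at each post-baseline visit and at any visit through Day 29, including early termination, regardless of the TEAE window.
3. Reconcile the flag with reported AESIs and list disagreements in both directions.
4. Keep the preferred-term tables as supportive.

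Cost: one derived variable and one table, plus the reconciliation. No new data, visits or patients.

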8.3.4.2 Relationship to Study Medication

Causality will be assessed according to the WHO Causality Assessment:

Related to IMP

Certain: Event or laboratory test abnormality, with plausible time relationship to drug intake. Cannot be explained by disease or other drugs. Response to withdrawal plausible (pharmacologically, pathologically). Event definitive pharmacologically or phenomenological (i.e. an objective and specific medical disorder or a recognized pharmacological phenomenon). Re-challenge satisfactory, if necessary.

Probable/Likely: Event or laboratory test abnormality, with reasonable time relationship to drug intake. Unlikely to be attributed to disease or other drugs. Response to withdrawal clinically reasonable. Re-challenge not required.

Possible: Event or laboratory test abnormality, with reasonable time relationship to drug intake. Could also be explained by disease or other drugs. Information on drug withdrawal may be lacking or unclear.

Unlikely: Event or laboratory test abnormality, with a time to drug intake that makes a relationship improbable (but not impossible). Disease or other drugs provide plausible explanations.

All AEs judged as having a reasonable suspected causal relationship to the IMP (i.e. possibly, probably, certain) will be considered as related to IMP. Any AE that is considered to be related to the IMP is described as an AR.

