8.3.10 Precautions/Overdose

The risk of overdosing in general in this study is considered to be very low. The planned maximum exposure will be approximately 0.066 mg/day of clobetasol propionate (approximately 0.924 mg of clobetasol propionate over a period of 14 days). The total amount of clobetasol propionate administered in the toxicological pre-clinical study (at the highest dose) was 4 times above the clinical trial dose, exhibiting no ocular toxicity. Systemic HED in pre-clinical study was 17-times higher compared to dosing in one eye of adults.

An expected AR that could represent a severe condition is the induction of IOP rise (and associated ocular pain and redness). In case of IOP >30mmHg, the investigator discretion is advised, using preferred standard of care at the study site. The use of specific ocular hypotensor eye drops (like beta blockers / alpha agonists / carbonic anhydrase inhibitors) is recommended.

Nevertheless, unintentional administration of any dose that deviates from the scheduled regimen will be documented and reported by center personnel.

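### SAP 6.3.10 identifies the instillation-pain AESI by two preferred terms plus relatedness, so as written it can leave out instillation events coded elsewhere and admit related eye pain that has no link to instillation

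*SAP*

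**What the plan says.** Protocol 8.3.9 names two AESIs. One is a pressure rise; the other is "Pain/discomfort associated with IMP instillation". The protocol ties the second to the act of instilling and lists no preferred terms for it. It also says that "the investigator is responsible for ensuring that all AESIs are reported to the Sponsor immediately", with a 24-hour limit.

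SAP 6.3.10 carries over the protocol's lead-in, "The following AEs (SOC, PT) of special interest (AESI) will be evaluated by Investigators at all study visits and time points (as applicable", and then specifies the pain AESI as "Pain/discomfort associated with IMP instillation (SOC-EYE DISORDERS, PT-EYE PAIN, OCULAR DISCOMFORT and related with IMP". Three conditions must therefore hold together: one system organ class (SOC), one of two preferred terms (PTs), and relatedness. The same section splits "relationship to treatment (No: not related, unlikely related, Yes: possible, probable and certain".

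The AESI results go into the overall TEAE summary (Table 14.3.1.1), the AESI table (14.3.1.9) and the related-AESI table (14.3.1.10).

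**The concern.** The protocol's concept depends on when and how the pain arose. The SAP's rule depends on how the event was coded and whether it was judged related. These can disagree in either direction, and the SAP gives no investigator report, verbatim search, timing rule or wider term group as another route into the AESI tables.

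Two side effects follow from putting relatedness inside the definition. First, for this AESI the table of all events and the table of related events cannot differ. Second, the condition refers to relatedness to IMP alone, while other lines of SAP 6.3.10 say IMP/Placebo. SAP 6.3.6.2 uses IMP as the label of the active arm. A literal programmer could exclude placebo events altogether.

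At stake is whether the stated count for one of the two AESIs, a local tolerability measure, matches what the protocol defined. No efficacy result is involved.

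**Working it through.** The documents state no AESI count or rate, so there is no plan figure to reproduce. The check compares definitions.

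**1. Can an instillation event be left out?** Inclusion in the SAP requires SOC Eye Disorders AND (Eye pain OR Ocular discomfort) AND related. Suppose an investigator reports pain on instillation under Protocol 8.3.9 and it is coded to any other PT or SOC. The second or first condition fails, so the event is not counted. The rule has no exception. Protocol 10.6 plans reconciliation between the safety and study databases for SAEs only, so a non-serious AESI report that does not match the coded rule would not surface there.

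**2. Can a non-instillation event be counted?** The related group starts at possible. Protocol 8.3.4.2 describes that category as a reasonable time relationship to the drug and adds: "Could also be explained by disease or other drugs". Neither part requires onset at instillation. An Eye pain event rated possible therefore meets all three conditions with no instillation link. The AE items listed in Protocol 8.3.3 and 8.3.7 include no instillation or AESI field that could remove it. Protocol 8.3.10 itself mentions drug-related eye pain with another origin: "An expected AR that could represent a severe condition is the induction of IOP rise (and associated ocular pain and redness".

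**3. Do the two AESI tables differ for pain?** Let A be the set of pain AESIs. By definition every member of A is related, so A restricted to related events is A. The pain rows of 14.3.1.9 and 14.3.1.10 must coincide, and the tables can differ only through the pressure AESI.

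**4. Scale.** Write T for patients with true instillation pain, s for the share of them coded outside the two terms, and f for patients with related eye pain but no instillation link. Then

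- counted = T(1 − s) + f
- error = f − T·s, which can have either sign.

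None of T, s or f is in the documents. Using the planned arm sizes (140 and 70, Protocol 9.1.1):

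- one misclassified clobetasol patient: 1/140 = 0.71 percentage points
- one misclassified placebo patient: 1/70 = 1.43 percentage points.

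Purely as an assumed range, true rates of 5% to 20% give T = 7 to 28 on clobetasol and 3.5 to 14 on placebo. With f = 0, s = 0 loses none, s = 0.5 loses half (3.5 to 14 on clobetasol) and s = 1 loses all. This shows the arithmetic of the rule and is not an estimate.

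**5. Placebo.** If relatedness to IMP were read as the active product only, the placebo pain count would be zero by construction, whatever T is. Protocol 6.4 keeps investigators masked, so causality ratings should exist for both arms. The wording still does not settle which reading applies.

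**The case against.** The best defence has four parts.

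- *The bracket may only describe expected coding.* The SAP keeps the statement that investigators evaluate AESIs, and the protocol already frames AESIs by SOC and PT. A reader might infer that the SAP discards the investigator's report. No text says so; the accurate statement is that the SAP gives the report no stated role in the count. If the bracket is only illustrative, the SAP does not say that either.
- *The pressure-related pain example is weak.* Protocol 8.3.7 asks for connected signs and symptoms to be reported together as one diagnosis where that can be done, so such pain would often sit under the pressure event. The visit descriptions in Protocol 4.3.2 also keep expected surgical pain out of the AE data. Both points reduce over-counting. Neither closes the route, since possible relatedness still needs no instillation link.
- *Nothing disappears from the report.* This stands. TEAEs are tabulated by SOC and PT (14.3.1.2.1), ocular events separately (14.3.1.2.2), related events in 14.3.1.5, and all AEs are listed (16.2.7.1). SAP 6.3.10 makes the safety comparison descriptive only.
- *The pain rows would nearly coincide anyway*, because pain on instillation is close to related by nature. That is fair, but agreement should then be a finding and not a consequence of the definition.

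**Conclusion.** The SAP's rule, read as written, does not match the protocol's AESI. It can misclassify events in both directions, makes two planned tables redundant for this AESI, and is ambiguous for placebo. It should be corrected. The consequence is limited to the descriptive AESI summaries; the primary and key secondary analyses are untouched.

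Stronger readings are tempting and are not supported:

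- That the AESI tables *are* wrong. The documents show only that they can be.
- That a particular number of events would be lost, or that particular other MedDRA terms would be used. The documents give no rate, coding split or term hierarchy.
- That local tolerability could not be read from the report. The other AE tables and the listing still show the events by arm or by patient, though without marking which arose on instillation.
- That this is the first ocular use of the product in humans. Protocol 2.1.4 says only that it had not been tried clinically in the proposed indications.

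The conclusion assumes that the bracket in SAP 6.3.10 will be programmed as an exhaustive definition.

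**What to change.** Before unmasking, amend SAP 6.3.10 as follows:

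1. Define this AESI as every event the investigator reported as instillation pain or discomfort under Protocol 8.3.9, plus events identified by masked review of AE verbatim terms, whatever the SOC or PT. Show the PT as description only.
2. Report related eye pain with no instillation link separately.
3. Apply the same rule to clobetasol and placebo, and say so.
4. Take relatedness out of the definition and use it only in Table 14.3.1.10 and the matching related-AESI line of Table 14.3.1.1.

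The listed AE items include no AESI or instillation field, so the rule should not presume a database flag. The Blind Data Review Meeting in SAP 6.2 is a natural place for the review, with the 8.3.9 reports set beside the coded events.

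The cost is a short masked review and a few lines of SAP text. The stated AESI rate may change. If unmasking has already taken place, the re-classification should be labelled post hoc in the study report, as Protocol 9.2 requires for such analyses.
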